2.7.4 Other safety data

2.7.4.1.1 ECG and cardiac imaging data

Changes in cardiac safety data such as ECG and echocardiogram are primary endpoints. For details, see Section 2.5.

ECG and echocardiogram results will be summarized descriptively by weight bracket and overall. Summaries according to QTcF notable ranges (QTcF > 500 ms) will be provided.

2.7.4.1.2 Vital signs

Changes in vital signs are primary endpoints. For details, see Section 2.5. Summaries according to abnormality assessments will be provided. Vital sign results will be flagged as clinically significant if they meet the pre-specified criteria which are defined in Appendix 5.6.

Height and weight will be measured (supine or standing) at each study visit. Screening weight shall be obtained \leq 14 days prior to Day 1. On Day 1, weight and height will be measured pre-dose. Changes in height, weight and body mass index will be presented in summary tables over time.

2.7.4.1.3 Neurological examination and sural sensory nerve action potential

Abnormal findings resulting from the examination of proprioceptive, vibratory, tactile and pain sensation will be summarized.

To complement neurological examination in case of clinically significant sensory abnormalities, sural sensory nerve action (SNAP) potential will be assessed. SNAP parameters include sural, median and peroneal SNAP voltage and velocity as well as overall interpretation, presented in data listings.

[figure not shown]
2.8 Pharmacokinetic endpoints

Not applicable.

2.9 PD and PK/PD analyses

Not applicable.

2.13 Interim analysis

An interim analysis will be performed once the last participant reaches the 6-month time point and will include all available data up until that data cut-off. The interim analysis is intended to provide an early safety readout from the study. No study design change or adaptation will be implemented based on the outcome of the interim analysis.

The interim analysis will cover all primary and secondary endpoints.

3 Sample size calculation

The size of approximately 24 participants is considered reasonable to provide descriptive safety information across 3 weight brackets ≥ 8.5 kg and ≤ 21 kg. A sample size of approximately 24 participants will provide 90% probability to observe at least one event if the underlying incidence of the event is 9%.

4 Change to protocol specified analyses

No change from protocol specified analysis was made.

5 Appendix

5.1 Imputation rules

Missing values for safety endpoints, including but not limited to AE, laboratory values, will not be imputed. For local lab, missing units or normal ranges will be reviewed by the medical team.

5.1.1 Study drug

If the date of study drug application will be missing or partial, it will be imputed by the date of the Day 1 visit.

Start time and duration of infusion of investigation drug will not be imputed if missing.

5.1.2 Date imputation

Missing or incomplete AE start and end dates will be imputed according to the general Novartis imputation rules.

Missing or incomplete dates of SMA diagnosis and of first symptoms will be imputed according to the general Novartis imputation rules.

Missing or incomplete start and end dates of medications will be imputed according to the general Novartis imputation rules.

Other data will not be imputed.

5.2 AEs coding/grading

Verbatim terms of AEs, including important identified and important potential risks, will be encoded by means of MedDRA according to the data management plan.

5.3 Laboratory parameters derivations

Hy's law criteria apply (see Section 2.7.3).

5.4 Statistical models

5.4.1 Analysis supporting primary objective(s)

Not applicable.

5.4.2 Analysis supporting secondary objective(s)

A mixed model of repeated measures is applied using unstructured covariance matrix as long as the model converges (compare Section 2.6.2). If the model does not converge with unstructured covariance matrix, heterogeneous compound symmetry of the covariance matrix will be assumed.

5.5 Rule of exclusion criteria of analysis sets

Table 1 Criteria leading to exclusion

Analysis Set	Criteria that cause subjects to be excluded
Enrolled Set	Not having informed consent; Screening failed
FAS, Safety Set	Not in Enrolled Set; No investigational drug taken

5.6 Clinically significant vital sign values

Vital sign results will be flagged as clinically significant if they meet the pre-specified criteria which are defined as follows.

Systolic and diastolic blood pressure:

- For participants aged <18 years at the time of assessment, systolic and diastolic blood pressure values \geq the corresponding to the 90th percentile value for age, gender, and height will be used to classify “high” clinically significant values according to Flynn 2017, Tables 4 for boys and 5 for girls, respectively.
 - Participants aged ≥ 2 to <3 years at the time of assessment will utilize the blood pressure levels defined for age 2 years, participants aged ≥ 3 to <4 years at the time of assessment will utilize the blood pressure levels defined for age 3 years, etc. For participants <2 years of age at the time of assessment levels defined for age 1 year apply.
 - Height percentile will be defined using the height at the time of assessment, or the most recently recorded height prior to the assessment if the height at the time of assessment is not available. Participants with a height which falls between two percentiles will be classified according to the lower of the two percentiles. Participants with height below the 5th percentile will be classified according to the 5th percentile.
- For all participants regardless of age at assessment, systolic blood pressure values below the 5th percentile will be classified as “low” clinically significant values. The 5th percentile value can be estimated as 70 mmHg plus twice participant’s age in years.

Temperature:

- For participants <18 years at the time of assessment, temperature values $\geq 38.4^{\circ}\text{C}$ will be classified as “high” clinically significant.
- For all participants regardless of age at assessment, temperature values $\leq 35^{\circ}\text{C}$ will be classified as “low” clinically significant.

Pulse rate:

The criteria for classifying high and low pulse rate values are contained in the table below. (Flemming 2011).

Age at assessment	High (bpm)	Low (bpm)
2 to <3 years	>128	<92
3 to <4 years	>123	<86
4 to <6 years	>117	<81
6 to <8 years	>111	<74
8 to <12 years	>103	<67
12 to <15 years	>96	<62
15 to <18 years	>92	<58

Weight:

- For participants <18 years at the time of assessment, weight values which reflect an increase from baseline of ≥ 2 BMI-for-age percentile categories (significant weight gain) will be classified as “high” clinically significant; weight values which reflect a decrease from baseline of ≥ 2 BMI-for-age percentile categories (significant weight loss) will be classified as “low” clinically significant.
 - Baseline BMI-for-age weight status categories are underweight (less than the 5th percentile), healthy weight (5th percentile to less than the 85th percentile), overweight (85th to less than the 95th percentile) and obese (equal to or greater than the 95th percentile).
 - BMI-for-age percentiles are obtained from the WHO Growth Charts (<https://www.who.int/toolkits/child-growth-standards/standards/body-mass-index-for-age-bmi-for-age> for 0 to under 5 years of age and <https://www.who.int/tools/growth-reference-data-for-5to19-years/indicators/bmi-for-age> for 5 to 19 years of age, respectively).

Respiratory rate:

The criteria for classifying high and low respiratory rate values are contained in the table below. (Flemming 2011; Eldridge 2014; Kou).

Age at assessment	High (breath/min)	Low (breath/min)
2 to <3 years	>34	<22
3 to <4 years	>29	<21
4 to <6 years	>27	<20
6 to <8 years	>24	<18
8 to <12 years	>22	<16
12 to <15 years	>21	<15
15 to <18 years	>20	<13

6 References

- Bayley N: The Bayley-III is a revision of the Bayley Scales of Infant Development – Third Edition (BSID-III), Technical Manual. San Antonio, TX: Harcourt, 2006.
- Eldridge L: What is a Normal Respiratory Rate? Updated May 16,2014.
- ICH E9 (R1) Harmonized Guideline: addendum on estimands and sensitivity analysis in clinical trials to the guideline on statistical principles for clinical trials. Final version on 20 November 2019.
- Kou R, Shuei L, Bradypnea, Department of Psychology, School of Medicine, National Yang-Ming University, Taipei, Taiwan.
http://rd.springer.com/referenceworkentry/10.1007%2F978-3-540-29676-8_246.

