Conditions that were already present at the time of informed consent should be recorded in medical history of the participant.

Adverse events (including lab abnormalities that constitute AEs) should be described using a diagnosis whenever possible, rather than individual underlying signs and symptoms.

Adverse event monitoring should be continued until end of study.

Once an AE is detected, it must be followed until its resolution or until it is judged to be permanent (e.g., continuing at the end of the study), and assessment must be made at each visit (or more frequently, if necessary) of any changes in severity, the suspected relationship to the interventions required to treat it, and the outcome.

Information about adverse drug reactions for the investigational drug can be found in the Investigator's Brochure (IB).

Abnormal laboratory values or test results constitute adverse events only if they fulfill at least one of the following criteria:

- they induce clinical signs or symptoms
- they are considered clinically significant
- they require therapy

Clinically significant abnormal laboratory values or test results must be identified through a review of values outside of normal ranges/clinically notable ranges, significant changes from baseline or the previous visit, or values which are considered to be non-typical in participant with the underlying disease.

On the basis of important identified and potential risks associated with OAV101, AESIs are determined and categorized as follows. These will be summarized based on Standardized MedDRA terminology:

- Hepatotoxicity
- Thrombocytopenia
- Cardiac adverse events
- Dorsal root ganglia toxicity
- Thrombotic microangiopathy

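### The blood pressure flag labelled 'clinically significant' ignores the child's baseline, so in this single-arm trial its count has no background rate to be read against

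*SAP*

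**What the plan says.** SAP 5.6 gives the limits. For children under 18, a systolic or diastolic value at or above the tabulated limit is high: "the corresponding to the 90th percentile value for age, gender, and height will be used to classify" such values. On the low side, "systolic blood pressure values below the 5th percentile will be classified as" low, and that limit is a formula: "The 5th percentile value can be estimated as 70 mmHg plus twice" the age in years.

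SAP 2.7.4.1.2 applies the limits: "Vital sign results will be flagged as clinically significant if they meet the pre-specified criteria which are defined in Appendix 5.6". On reporting it adds: "Summaries according to abnormality assessments will be provided". Neither section asks for a change from baseline, a normal baseline value or a repeat reading for blood pressure. Neither says whether flags are counted per visit or per child, or that the share of children beyond the limits at baseline will be shown.

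Elsewhere the SAP does use baseline. The weight flag in 5.6 is relative to it ("weight values which reflect an increase from baseline of" at least two BMI categories). SAP 2.5.2 and 2.7.3 give laboratory data shift tables against it. SAP 2.5.2 also summarises mean change from baseline in vital signs, but that does not enter the flag.

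**The concern.** A percentile limit marks a fixed share of healthy readings by construction. Without the child's own starting position, a flag after dosing may be a new rise, a level the child already had, or ordinary variation.

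This matters here for two reasons. The trial has one arm, so no comparator supplies the background rate. And Protocol 4.6 lists raised blood pressure among the risks of corticosteroids, which every child receives from 24 hours before infusion. Vital signs belong to a primary safety endpoint, and this table is where a blood pressure signal would be looked for. A reader shown, for example, 4 of 24 children flagged high at a visit cannot tell whether that exceeds what the same children showed before treatment.

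**Working it through.** The plan states no expected flag rate, so there is no figure of its own to reproduce on this point.

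**Inputs from the documents.** High limit: 90th percentile for systolic (SBP) and for diastolic (DBP). Low limit: estimated 5th percentile, SBP only (SAP 5.6). Follow-up visits: 11, Week 1 to Week 52 (SAP 1.1), with vital signs at each visit (SAP 2.5.1). Participants: about 24 (SAP 3).

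**Assumptions not in the documents.** The children follow the reference distribution; readings are normal on that scale; SBP–DBP correlation is 0.5; correlation between a child's visits is 0.3–0.7, with 0.9 as an extreme.

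**Step 1: one visit, no effect.**
- P(high SBP) = P(high DBP) = 0.10. At correlation 0.5, P(both high) = 0.032.
- P(any high) = 0.10 + 0.10 − 0.032 = 0.168, about 17%.
- Low SBP adds 0.05; its overlap with high DBP is negligible (below 0.001). P(any flag) = 0.168 + 0.05 = 0.218, about 22%.
- Of 24 children: 24 × 0.168 = 4.0 high and 24 × 0.218 = 5.2 with any flag, at every visit.
- With SBP–DBP correlation between 0.3 and 0.7, any flag is 20–23%.

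**Step 2: per child over 11 visits, if counted that way.** With independent readings, high SBP alone gives 1 − 0.90^11 = 69%, and high or low SBP gives 1 − 0.85^11 = 83%. Readings on one child are correlated, so SBP and DBP were simulated with a child-level random effect (100,000 children per setting, no effect):

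| Within-child correlation | Ever high | Ever any flag |
|---|---|---|
| 0.3 | 70% | 87% |
| 0.5 | 59% | 78% |
| 0.7 | 47% | 64% |
| 0.9 | 33% | 44% |

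**Step 3: response to a real rise.** Shift both pressures by +0.5 SD. P(high) per parameter becomes 0.217 and P(both) 0.098, so P(any high) = 0.217 + 0.217 − 0.098 = 0.336. The per-visit high rate doubles, from 17% to 34%. Ever high over 11 visits goes from 47–70% to 71–91%. Pooling high with low hides part of this, because the shift removes low flags while adding high ones: ever any flag goes only from 64–87% to 77–94%.

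**Step 4: what baseline adds.** With no effect the expected share beyond the limit is the same at baseline and at each visit, so moves out of range and moves into range balance in expectation. A baseline column and a shift table therefore supply the missing comparator. Counting children ever newly flagged does not by itself remove the background: among all children, 44–67% are unflagged at baseline and flagged at some later visit (correlation 0.7 to 0.3). Requiring a high that is new against baseline and repeated at the next visit lowers this to 13–16% with no effect, against 35–43% at +0.5 SD.

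**The case against.** The strongest reply is that the flag is a secondary display. Mean change from baseline in vital signs is already summarised by weight bracket and overall, all individual data are listed, and SAP 2.1 makes the analysis visit the default unit. The SAP does not specify an ever-flagged count, and it classifies high and low separately. The liver criteria in SAP 2.7.3 are also counted regardless of baseline. All of this stands. It makes the per-visit 17% the firmer figure and the per-child figures conditional. It does not supply the background share.

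Four stronger readings are tempting, and the documents do not support them.

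- A reader might infer that the flag can neither reassure nor warn. Step 3 contradicts this: the per-visit high rate doubles under a half-SD rise.
- A reader might infer that flagged values become adverse events, because Protocol 10.1.1 lists test results where "they are considered clinically significant" as an AE criterion. There the judgement comes from a review that considers change from baseline or the previous visit, and the investigator identifies AEs. A programmed flag creates no AE; only the wording overlaps.
- A reader might infer that rounding inflates the high rate, since "Participants with a height which falls between two percentiles will be classified according to the lower of the two percentiles". The same list moves heights below the 5th percentile up to it, which points the other way. The direction and size of the height and age effects depend on tables that are not in the documents.
- A reader might want only confirmed, new values counted. From Week 13 the visits are about 13 weeks apart, so confirmation could require a rise lasting three months. The SAP baseline is the last value before infusion, after prednisolone has started, so a child already raised on steroid would drop out of such a count.

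**Conclusion.** The point holds in a limited form. The blood pressure flag uses one reading and no baseline, and under the reference distribution it marks about 17% of children high and about 22% in some direction at each visit with no effect. If flags are counted per child over 11 visits, that becomes 47–70% and 64–87% at within-child correlation 0.3–0.7.

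It would be too strong to say that most children will be flagged. That needs a per-child count, which the SAP does not set. It fails for any flag at correlation 0.9 (44%) and for high flags alone at 0.7 (47%). The documents give neither the correlations nor evidence that symptomatic children with SMA match the reference population, and the 5% low rate rests on a limit that is itself an estimate.

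The consequence is confined to reading a descriptive safety table. No test, sample size or change-from-baseline summary is affected.

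**What to change.** In SAP 2.7.4.1.2 and 5.6:

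1. Summarise high and low blood pressure flags separately, by visit, weight bracket and overall, and state the counting unit.
2. Print the proportion beyond each limit at baseline beside each visit. Also print the proportion at screening, because the SAP baseline can fall after the first prednisolone dose. The vital-signs row of Table 8-1 was not legible in the text available to me, so confirm that a screening reading is collected.
3. Add a shift table from baseline, or a count of flags new against baseline, as the laboratory data already have. The shift table is preferable because it shows movement in both directions.
4. Label these results 'outside reference limits', so they are not confused with the investigator's judgement in Protocol 10.1.1.
5. Optionally add a count of new values confirmed at the next scheduled visit, as a supplement and not a replacement, noting the wide spacing of late visits.

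The cost is SAP wording and a few table derivations. If the screening reading is collected as expected, no new data are needed. The limits stay as they are, every single excursion stays in the listings, and clinical management does not change.

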5.2 Exclusion criteria

Participants meeting any of the following criteria are not eligible for inclusion in this study.

1. Previous OAV101 use or previous use of any AAV9 gene therapy
2. BMI < 3rd percentile based on WHO Child Growth Standard
3. Participant with history of aspiration pneumonia or signs of aspiration (e.g., coughing or sputtering of food) within 4 weeks prior to screening
4. Anti-AAV9 antibody titer > 1:50 as determined by ligand binding immunoassay at the time of screening
5. History of gene therapy, hematopoietic transplantation, or solid organ transplantation
6. Inability to take corticosteroids
7. Concomitant use of immunosuppressive therapy, plasmapheresis, immunomodulators such as adalimumab, or immunosuppressive therapy within 3 months prior to gene replacement therapy (e.g., cyclosporine, tacrolimus, methotrexate, rituximab cyclophosphamide, IV immunoglobulin)
8. Requiring invasive ventilation, tracheostomy or awake non-invasive ventilation (standard of care nocturnal BiPAP is not considered exclusionary)
9. Administration of vaccines 2 weeks prior to infusion of OAV101
10. Awake hypoxemia (O₂ saturation <95%) or awake oxygen saturation level decrease between screening and dosing that is clinically significant, as per investigator judgment.
11. Clinically significant neurologic or neuromuscular conditions other than SMA as determined by the principal Investigator
12. Clinically significant abnormalities in laboratory test results at Screening as determined by the Investigator
13. Hepatic dysfunction (i.e. AST, ALT, bilirubin, GGT or GLDH, > ULN) at Screening (with the exception of isolated AST elevation: in the absence of other liver laboratory abnormalities, isolated AST elevation is not considered exclusionary)
14. Excluding SMA, any medically unstable condition considered clinically significant by the Investigator, including cardiomyopathy, hepatic dysfunction, kidney disorder, endocrine disorder, GI disorders, metabolic disorders, severe respiratory compromise and significant brain abnormalities at either Screening or Baseline that, in the opinion of the Investigator, would interfere with the overall interpretation of safety or efficacy of the study
15. Presence of a confirmed or suspected active infectious process from screening and up to dose administration
16. If previously treated with disease modifying therapy, participants are excluded if they received
 - less than 3 doses of nusinersen (Spinraza[®])

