2.5.2 Statistical hypothesis, model, and method of analysis

No hypothesis testing will be performed.

Incidence and severity for treatment emergent AEs and SAEs as well as important identified and important potential risks will be summarized by weight bracket and overall in the safety set. The number and proportion of participants reporting a treatment emergent AE or SAE at least once will be reported. Summaries will also be provided by MedDRA System Organ Class and Preferred Term.

Changes from baseline in vital signs and clinical laboratory results will be summarized descriptively by weight bracket and overall in the safety set. Mean, standard deviation, median, minimum, and maximum will be presented. For each applicable time point, only participants with a baseline value and a measurement for that time point will be included in the summary. Shift tables of laboratory abnormality versus baseline will be provided for minimum, maximum and final post-baseline values. For laboratory parameters of primary interest except for GLDH, direct and indirect bilirubin, additional shift tables will consider CTCAE grading, version 5. For troponin-I, any value above the upper limit of the reference range (ULN) is considered CTCAE Grade 1. Number of participants with ALT >ULN, 2xULN, 3xULN per visit will be summarized. Individual courses of and median changes from baseline in clinical laboratory results of ALT, AST, GLDH, ALP, GGT, serum total bilirubin, direct bilirubin, indirect bilirubin, platelets, and troponin-I over time will be visualized. Graphs of median changes will be per weight bracket. Graphs of individual clinical laboratory results will use normalized values as multiples of ULN.

Procedure results including ECG QTcF and overall interpretation will be summarized descriptively by weight bracket and overall.

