2.6 Analysis supporting secondary objectives

2.6.1 Secondary endpoint(s)

The secondary endpoints include:

1. Changes from baseline in HFMSE and RULM;
2. Percent of participants achieving development motor milestones according to the WHO-Multicenter Growth Reference Study (WHO-MGRS) and Bayley Scale of Infant and Toddler Development - Third Ed (Bayley-III) criteria.

For all participants of 24 months of age or more at the time of visit, HFMSE (2019 edition) will be assessed, consisting of 33 SMA-specific items with a maximal total score of 66 (O'Hagen et al 2007). Each item is scored on a 3-point Likert scale from 0 (no response) to 2 (full response) and summed up to the total score. A higher score indicates a higher ability level. A total score will not be derived if any item score is missing or "cannot test".

For all participants of 30 months of age or more at the time of visit, RULM will be assessed, consisting of 19 items with a maximal total score of 37 with lower scores reflecting poorer ability. RULM is an assessment that measures motor performance in the upper limbs from childhood to adulthood in ambulatory and non-ambulatory individuals with SMA. There are 18 items scored 0 (unable) to 2 (full achievement) and one item scored 0 (unable) to 1 (able) summed up to the total score (Pera et al 2019). For participants of 24 to 30 months of age at the time of visit, the two test items (C)- Tracing a path and (H)- Tearing Paper will not be administered and therefore for a participant between the ages of 24-30 months the maximum score achieved is 33 points. A total score will not be derived if any item score is missing or "cannot test".

Changes from baseline are only summarized for subjects whose baseline values are available. For younger subjects who are not eligible for RULM/HFMSE measure at baseline, their scores at later visits will only be listed.

The Developmental Milestone Checklist consists of 10 Developmental Motor Milestones obtained from WHO-MGRS (sitting without support, hands-and-knees crawling, standing with assistance, walking with assistance, standing alone, and walking alone) and from Bayley-III (head control (Bayley gross motor item #4), sits with slight support for at least 30 seconds (Bayley gross motor item #19), sits without support for at least 30 seconds (Bayley gross motor item #26), and pulls to stand (Bayley gross motor item #35)) (WHO Multicentre Growth Reference Study Group 2006, Bayley 2006).

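### The SAP's weight flag cannot register loss from a baseline BMI below the 85th percentile, or gain from a baseline at or above it; the pulse and respiratory-rate flags have no rule before age 2

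*SAP*

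**What the plan says.** SAP 2.7.4.1.2 applies individual flags to vital signs: "Vital sign results will be flagged as clinically significant if they meet the pre-specified criteria which are defined in Appendix 5.6". The same section promises summaries by abnormality assessment.

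For weight, Appendix 5.6 calls a result high after a rise from baseline of at least two categories. After a fall of at least two, values in "BMI-for-age percentile categories (significant weight loss) will be classified as" low. The appendix defines four categories: "underweight (less than the 5th percentile), healthy weight (5th percentile to less than the 85th percentile"), then "overweight (85th to less than the 95th percentile) and obese (equal to or greater than the 95th percentile").

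For pulse and respiratory rate, Appendix 5.6 gives tables by age at assessment. Both begin with the row for 2 to under 3 years, and neither has a fallback for younger children. The blood-pressure rule in the same appendix does have one: it applies the age-1 levels before the second birthday.

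Young children can enter. Protocol 5.1 sets weight limits and no age limit. Protocol 8.5.1.1 describes participants under 24 months who start HFMSE only when they reach that age. SAP 2.6.1 says: "For younger subjects who are not eligible for RULM/HFMSE measure at baseline, their scores at later visits will only be listed".

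**The concern.** A flag labelled as significant weight loss should be able to fire for any child who loses a large amount of weight. With four categories and a two-category threshold, whether it can fire depends on where the child started, not on how much was lost. A table showing no child flagged low would read as no significant loss, even if few children could have been flagged at all.

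The same applies to gain for heavier children. Protocol 4.6 lists Cushing's syndrome and salt and water retention among the corticosteroid risks, so a gain flag that is blind from the 85th percentile upward is also a loss of information.

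For pulse and respiratory rate before age 2, the SAP does not say how an assessment is classified. A programmer could leave it blank, count it as normal, or borrow the row for 2 to under 3 years. Blank and normal give the same count of flags but different denominators, and borrowing the row can change the count.

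**Working it through.** The plan gives no figure of its own here, so there is none to reproduce. The first step uses only the SAP's text; the BMI shares and dosing ages below it are assumptions.

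**Which shifts can trigger a weight flag.** Number the categories 1 (under 5th), 2 (5th to under 85th), 3 (85th to under 95th) and 4 (95th and above). Low requires baseline minus post-baseline of at least 2; high requires post-baseline minus baseline of at least 2.

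| Baseline | Shifts that trigger low | Shifts that trigger high |
|---|---|---|
| 1 underweight | none | to 3 or 4 |
| 2 healthy | none (largest fall is 1) | to 4 |
| 3 overweight | to 1 | none (largest rise is 1) |
| 4 obese | to 1 or 2 | none |

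Of the 16 baseline-by-follow-up pairs, 3 trigger low and 3 trigger high. Low is impossible from below the 85th percentile, and high is impossible from the 85th upward.

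**Size of change against the flag.** Standard normal quantiles: 0.1st = -3.090, 5th = -1.645, 84.9th = 1.032, 94.9th = 1.635, 95th = 1.645.

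- Rise from the 84.9th to the 95th: 1.645 - 1.032 = 0.61 z, flagged.
- Rise from the 5th to the 94.9th: 1.635 + 1.645 = 3.28 z, not flagged.
- Fall from the 95th to the 84.9th: 0.61 z, flagged.
- Fall from the 84.9th to the 0.1st: 1.032 + 3.090 = 4.12 z, not flagged.

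**How many children this could touch.** Baseline BMI is not in the documents. Protocol 5.2 excludes "BMI < 3rd percentile based on WHO Child Growth Standard". Assume that BMI otherwise follows the WHO reference:

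- Never flaggable for loss: (85 - 3)/(100 - 3) = 82/97 = 85%.
- Never flaggable for gain: 15/97 = 15%.
- Expected number who could be flagged for loss: 24 × 15/97 = 3.7, or 30 × 15/97 = 4.6.
- Chance that a weight bracket holds no child who could be flagged for loss: 0.845^6 = 0.36 with 6 children, 0.845^10 = 0.19 with 10.

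If BMI z is normal with SD 1 and its mean is shifted (also an assumption), the share never flaggable for loss, given entry at or above the 3rd percentile, is:

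| Mean BMI z | Share |
|---|---|
| -1 | 97% |
| -0.5 | 93% |
| 0 | 85% |
| +0.5 | 70% |

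**Pulse and respiratory rate.** The follow-up visits have nominal days 8, 15, 22, 29, 43, 57, 71, 92, 183, 274 and 365, which is 11 visits. At 30.4375 days per month, the visits before the second birthday, for illustrative ages at dosing, are:

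| Age at dosing | Days to age 2 | Visits with no rule |
|---|---|---|
| 14 months | 10 × 30.4375 = 304.4 | 10 of 11 (to Week 39) |
| 20 months | 4 × 30.4375 = 121.8 | 8 of 11 (to Week 13) |
| 22 months | 2 × 30.4375 = 60.9 | 6 of 11 (to Week 8) |

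The documents do not say how many such children are expected.

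**The case against.** The strongest reply is that little depends on these flags. The study is single-arm with no hypothesis testing, and the main vital-sign analysis does not use them: "Changes from baseline in vital signs and clinical laboratory results will be summarized descriptively by weight bracket and overall in the safety set", with minimum and maximum. In addition, "Changes in height, weight and body mass index will be presented in summary tables over time". All individual data are listed, and clinically significant findings become AEs through the investigator, not through this flag. A large loss would therefore show elsewhere. This stands, and it limits the point to the flag displays. It does not rescue them: in brackets of 6 to 10 children an individual-level flag is there to point to the one child whose change a mean can hide.

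A second reply concerns wording. The rule counts percentile categories, while the four bands are introduced as baseline weight-status categories, so another set may have been meant. No other set is defined, so the four-band reading is the only one the SAP supports. If another was intended, the SAP has to state it.

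A third is that, read literally, a pulse or respiratory-rate result with no table row meets no criterion and is simply not flagged. That is a fair reading of the count, but it leaves open whether the child belongs in the denominator.

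Finally, SAP 2.6.1 is weak support on its own for children under 2, because its younger subjects may include those aged 24 to 30 months for RULM. Protocol 8.5.1.1 and the blood-pressure rule for under-2s settle the matter without it. The percentile contrasts above are constructed extremes, and the structural result does not depend on them.

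**Conclusion.** The point holds. The weight result follows from the SAP's four categories and two-category threshold, and is true for any enrolled sample: no low flag from a baseline below the 85th percentile, no high flag from the 85th upward. Its size is conditional. About 85% of children would be unflaggable for loss under the WHO reference, with a range of 70% to 97% for mean BMI z from +0.5 to -1 with SD 1; none of these inputs is given in the documents.

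The gap before age 2 for pulse and respiratory rate is also real, with the number of children affected unknown. The consequence is confined to the flag-based summaries of SAP 2.7.4.1.2. The rule should be corrected before those tables are produced, because a zero in the low column for weight would otherwise carry reassurance that it has not earned.

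**What to change.** Replace the two-category weight rule in Appendix 5.6 with a change from baseline in WHO BMI-for-age z-score, or a count of percentile lines crossed, that can register both loss and gain from any baseline. The cut-off should be chosen by the sponsor's clinicians and stated in the SAP.

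For pulse and respiratory rate, either state a rule for assessments before age 2, as blood pressure already has, or report these assessments as not classifiable and leave them out of the flag denominators.

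The cost is appendix wording and programming, using height, weight and age that are already collected. The one downside is that more flags will be reported.
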